Primary Endpoints	
1. TICI using NEWS Score [Time Frame: First treatment date up to discharge day (PI's discretion as per patients health condition)]
 
The median time in days from the start of treatment with the study drug / placebo to the persistent achievement of all of the following criteria:
 
 • Stopping a fever (which is defined as a decrease in axillary temperature below 37 ° C without the use of anti pyretic drugs); • Respiratory rate <22 /min; • Oxygen saturation (SPO2) > 95% when breathing in atmospheric air. Measured using pulse oximetry • Systolic blood pressure ≤200mmHg • Pulse rate 51-90beats/minute • Is conscious and alert 
[Note: Persistent achievement means the preservation of each of the criteria for at least 7days.]
 
2. TTIC using 7-point ordinal scale
 
3. Rate of progression to severe/critical COVID-19 disease based on NEWS score [Time frame: First treatment date up to 15days]
 
4. Rate of progression to severe/critical COVID-19 disease based on 7-point ordinal scale [Time frame: First treatment date up to 28days]
 
5. Time to COVID-19 nucleic acid testing negativity in oropharyngeal/nasal swab) [Time Frame: First treatment date up to 28days]

Secondary Endpoints	
 1. Incidence of ICU admissions [Time Frame: 28days] 2. Subject survival rate [Time Frame: 28days] 3. Incidence of mechanical ventilation due to COVID-19 infection [Time Frame: First treatment date up to 28days] 4. Change in clinical or laboratory assessment of comorbid condition [Time Frame: First treatment date up to 28days] 5. Percent of participants with worsening comorbid condition [Time Frame: First treatment date up to 28days] 6. Proportion of subjects in the treatment arm who had AE, SAE 7. Proportion of subjects in the placebo arm who had AE, SAE
Subject Selection Criteria	
Inclusion criteria
 
 1. 50 years or older

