Stopping the Study Drug	
 1. Completing 14 days of treatment 2. Progression to severe COVID-19: ViraCide will be stopped if subjects progresses to severe COVID-19 and require ICU admission, mechanical ventilation and any such situation where according to the PI the subject

	
cannot continue ViraCide. However, subject will be followed-up to capture data on ICU admission, incidence and mortality
 
 3. Progression of comorbid condition requiring admission to ICU or inability of the subject to take anything orally. However, subject will be followed-up to capture data on ICU admission, incidence and mortality 4. Subject's participation to the study is terminated 5. Study is terminated
Termination of Subject's Participation in the Study	
Any participant can be removed from the study:
 
 1. By his/her own free will to not continue in the study. Subject withdrawal of informed consent. 2. Loss of contact with the subject during the study. 3. Does not comply with dosing schedule (75%-125% non-compliance) 4. The development of AE / SAE requiring the withdrawal of the study drug. However all AE / SAE will be followed-up till the study duration 5. Pregnancy confirmed anytime during the study duration 6. Another reason, which, according to the PI, requires the termination of the subject's participation in the study.
Study Termination	
The study can be terminated if
 
 1. There is a major deviation in Protocol 2. Another reason, which, according to the PI, requires study termination

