5. Time to COVID-19 nucleic acid testing negativity in oropharyngeal/nasal swab) [Time Frame: First treatment date up to 28 days]

Confidential & Proprietary

The unauthorized use, disclosure, distribution or copying of these information is strictly prohibited

Secondary Efficacy Endpoints:

1. Incidence of ICU admissions [Time Frame: 28 days]
2. Subject survival rate [Time Frame: 28 days]
3. Incidence of mechanical ventilation [Time Frame: First treatment date up to 28 days]
4. Time to COVID-19 nucleic acid testing negativity in oropharyngeal/nasal swab) [Time Frame: Days 1, 7, 15]
5. Change in clinical or laboratory assessment of comorbid condition [Time Frame: First treatment date up to 28 days]
6. Percent of participants with worsening comorbid condition [Time Frame: First treatment date up to 28 days]

Safety Endpoints

1. Proportion of subjects in the treatment arm who had AE, SAE
2. Proportion of subjects in the placebo arm who had AE, SAE

Confidential & Proprietary

Any unauthorized use, disclosure, distribution or copying of these information is strictly prohibited

3 Analysis sets

Per protocol subset (PP)

Subjects without any Major protocol violation would be included in the per-protocol population, including those subjects who have completed all the visits, who did not take any prohibited medications during the study period and whose CRF was completed as requested.

Modified Intention to treat subset (mITT)

The term “mITT” includes all randomized subjects who met all inclusion/exclusion criteria, administered at least one dose of assigned product with at least completed one visit will be included in the mITT population.

Safety analysis subset

The safety population will consist of all subjects enrolled in the study, who have received at least one dose of study products i.e. mITT population.

Methods of Analysis

Primary Efficacy and secondary endpoints will be analyzed using the PP & mITT population. And Safety variables as per mITT only.

4 Data Handling

Data entry into CRF must be performed as per general CRF data entry guidelines, summarized at the time of data entry feasibility training. Data entry will be made as per source document without interpretation or modification to maintain consistency and accuracy of the data. Study specific

Confidential & Proprietary

Any unauthorized use, disclosure, distribution or copying of these information is strictly prohibited

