5.1 Descriptive methods

Participant Disposition

Demographic and Baseline Information

Continuous variables that are Age, weight, BMI, and other demographical characteristics will be summarized by overall using summary statistics i.e. the number of observations, mean and standard deviation with 95% CI (among normal distribution) or median with range (if non-normal distribution). Categorical values like gender and clinical Examination will also be summarized using frequencies and percentages.

Confidential & Proprietary

Any unauthorized use, disclosure, distribution or copying of these information is strictly prohibited

The medical history and Physical examination will be presented using frequencies and percentages of subjects for the Safety population. For continuous data student analysis of variance test and for categorical data Chi square test will be estimated to compare the baseline demographical data between groups and changes during the follow up.

5.2 Efficacy Parameters:

Summary of efficacy parameters – the number of observations, mean and standard deviation with 95% CI (among normal distribution) or median with range (if non-normal distribution)

Analysis of Primary Efficacy Parameters

In this study median Time to Clinical Improvement (TTCI) using NEWS Score [Time Frame: First treatment date up to when PCR is negative] TTIC using 7-point ordinal scale [Time Frame: First treatment date up to when PCR is negative] will be assessed for both Test and Placebo group and compare the mean time between two arms by using Mann Whitney U test.

Other variables that are Rate of progression to severe/critical COVID-19 disease based on NEWS score and 7 point ordinal scale [Time frame: First treatment date up to 28 days] will be compared by using Chi Square test.

Other parameter like Time to COVID-19 nucleic acid testing negativity in oropharyngeal/nasal swab) [Time Frame: First treatment date up to 28 days] will be estimated by Student t test or one way analysis of variance. If data is

Confidential & Proprietary

Any unauthorized use, disclosure, distribution or copying of these information is strictly prohibited

not passing normality for continuous variable Mann Whitney test will be assessed instead of student t test.

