5.3 Analysis of Secondary Efficacy Parameters

For Secondary efficacy variables that is Incidence of ICU admissions, subjects survival rate , incidence of mechanical ventilation , percentages of participants with worsening co morbid conditions and changes in clinical comorbid conditions will be analyzed using Chi square test variance (Kruskal Wallis test) for between Groups. If observed mean difference is significant Friedman's post hoc test will be applied to assess which group is significant. Average Time to COVID-19 nucleic acid testing negativity in oropharyngeal/nasal swab) will be assessed at each time points and data will be analyzed by using analysis of variance. If data is not normal, analysis of variance with kruskal wallies will be estimated.

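### Three primary endpoints are times to an event, but the SAP gives no censoring rule, worst rank or other value for subjects without the event, and its t test, ANOVA and mean-time tables cannot include them

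*SAP*

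**What the plan says.** **Tests.** For both TTCI endpoints, SAP 5.2 will "compare the mean time between two arms by using Mann Whitney U test". Time to PCR negativity "will be estimated by Student t test or one way analysis of variance", with Mann-Whitney if normality fails. SAP 5.3 returns to PCR time as a secondary endpoint: "Average Time to COVID-19 nucleic acid testing negativity in oropharyngeal/nasal swab) will be assessed at each time points", by ANOVA or Kruskal-Wallis. SAP 6 plans tables of mean times. SAP 5.2 summarises efficacy by mean and SD, or median and range.

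**Who is analysed.** The mITT set in SAP 3 takes eligible randomised subjects "administered at least one dose of assigned product with at least completed one visit". The protocol synopsis foresees subjects without an event. After progression the study drug stops but the "subject will be followed-up to capture data on ICU admission, incidence and mortality", and participation may end through "Loss of contact with the subject during the study".

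**Windows.** For NEWS TTCI the protocol's time frame is "First treatment date up to discharge day", at the investigator's discretion. SAP 2 and 5.2 end it at PCR negativity instead. The protocol adds that "Persistent achievement means the preservation of each of the criteria for at least 7days".

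**Schedule.** After baseline, the protocol lists NEWS and 7-point scores on Days 7 and 15 and a telephone call on Day 28. It lists one on-study swab, on Day 15 or at earlier discharge, and no laboratory work on Days 1 and 7. SAP 2 gives Days 1, 7 and 15 for the secondary PCR time.

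**What is absent.** Neither document mentions censoring, Kaplan-Meier, log-rank, worst rank or imputation. SAP 4, on data handling, covers CRF entry and site files only.

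**The concern.** A t test, an ANOVA or a mean needs a number for every subject. A subject who has not improved or turned negative by the end of observation has no number, only a lower bound. The mITT set admits such subjects and the plan does not say what to do with them, so someone must decide later, possibly after unblinding.

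The choice matters because failing to improve is itself an outcome. If subjects without an event drop out of the comparison, it covers only those who improved. An arm in which more subjects fail can then look the same as one in which fewer fail.

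**Working it through.** **1. The plan's own figure.** The protocol gives 112 completed subjects (56 per arm) at 80% power and 5% significance, and 124 enrolled after 10% dropout. 112 × 1.10 = 123.2 and 112 / 0.90 = 124.4, so 124 reproduces to within one subject. The 112 cannot be reproduced, because no effect size, SD, event rate or test is given. The inputs below are therefore assumptions.

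**2. Which planned methods can take a subject without an event?**

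| Planned method | Endpoint | Can it include the subject? |
|---|---|---|
| t test, ANOVA, mean tables | PCR time (5.2, 5.3); mean tables also for TTCI | No, unless a value is assigned; none is stated |
| Mann-Whitney, Kruskal-Wallis | TTCI; fallback for PCR time | Yes, with a tied worst rank; none is stated |

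The time frames do not fill the gap. For NEWS TTCI they conflict, neither end is a fixed day, and the SAP window never closes for a subject who stays PCR positive.

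**3. Illustration of size.** Assumed: 56 per arm, exponential times, hazard ratio for improvement 1.75, control median m = 10, 7 or 5 days, nobody meeting the criteria on Day 1, times known to the day for 28 days. Two-sided 5%, tie-corrected Mann-Whitney, 20,000 simulated trials per case.

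Share with no event by day 28: control 0.5^(28/m), active 0.5^(1.75 × 28/m).

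| Control median (days) | 10 | 7 | 5 |
|---|---|---|---|
| No event, control | 0.5^2.8 = 14.4% | 0.5^4 = 6.3% | 0.5^5.6 = 2.1% |
| No event, active | 0.5^4.9 = 3.3% | 0.5^7 = 0.8% | 0.5^9.8 = 0.1% |
| Power, subjects dropped | 40% | 56% | 67% |
| Power, worst rank | 71% | 71% | 72% |
| Power, log-rank | 81% | 82% | 83% |

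At hazard ratio 1 every method rejects about 5% of the time. The gap between dropping and a worst rank shrinks from 31 points to 5 as fewer subjects lack an event.

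**4. A difference only in failure to improve.** Assume 70% of control and 90% of active subjects ever improve, at the same speed (median 7 days among improvers), over 28 days (4,000 trials). By day 28 about 34% and 16% have no event, yet the mean time among improvers is 8.8 against 8.7 days. Power is 5% with subjects dropped, 42% with a worst rank and 57% with log-rank.

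**5. Sensitivity to Day 1 status.** Eligibility admits asymptomatic subjects, and mild cases must have SpO2 above 95%, so some may meet the criteria at baseline. With scoring only 6 and 14 days after Day 1 and the other inputs as in step 3, power across the three medians is 12-33% (dropped), 65-70% (worst rank) and 69-75% (log-rank). If 30% meet the criteria on Day 1, these fall to 5-7%, 18-20% and 31-35%.

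**6. NEWS TTCI on the listed scores.** Seven days of persistence from Day 15 runs past the last listed score. After baseline, only an improvement present on Day 7 and still present on Day 15 can be confirmed. That leaves one possible post-baseline event day. Log-rank and worst-rank Mann-Whitney then make the same yes/no comparison: with the inputs of step 3 and improvement counted at Day 7 only, both give about 50/59/66%.

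**7. PCR time.** With one swab, as the protocol lists it, the time of a subject negative at that swab is simply the swab day, which discharge can bring forward. The true time lies somewhere between baseline and that swab.

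**The case against.** The strongest reply is that for TTCI the SAP names a rank test, which takes non-improvers as tied worst ranks. On that view the defect is one missing sentence. That stands: for two of the three endpoints the test is usable and the rule is missing. It does not rescue the t test, ANOVA or mean tables.

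A reader might infer that the SAP intends to exclude subjects without an event. It does not say so; it is silent, and dropping them is only one possible default. A reader might also infer a raised false-positive rate. The simulation does not support that when the arms do not differ.

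A third inference is that a log-rank test restores power. It need not: step 5 shows low power for every method if many subjects meet the criteria at baseline, and step 6 shows no gain for NEWS TTCI on the listed scores.

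The schedule is read from a synopsis. Subjects are managed in isolation wards and the CRF can draw on the patient file, so more frequent scores may exist; neither document lists them. Finally, the chi-square tests on progression (primary endpoints 3 and 4) count some failures, but they do not supply a rule for the time endpoints.

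**Conclusion.** The concern holds and should be fixed before unblinding. As written, the t test, ANOVA and mean comparisons cannot use all mITT subjects, and the Mann-Whitney comparisons can do so only with a rule that the SAP omits.

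In the 28-day illustration, dropping subjects costs about 5 to 31 points of power against a worst rank and about 16 to 41 against log-rank. Those figures rest on an assumed hazard ratio, assumed medians, daily data that the protocol does not list, and nobody meeting the criteria on Day 1. They show that the missing rule can decide the result; they do not predict this trial's power. The loss is small if few subjects lack an event.

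The documents do not support saying that Mann-Whitney is the wrong test for TTCI.

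**What to change.** 1. **SAP 5.2, 5.3 and the mean-time tables.** Drop the t test, ANOVA and mean comparisons. Analyse all mITT subjects by Kaplan-Meier, a log-rank test and a hazard ratio, in forms suited to discrete or interval-censored times. Mann-Whitney with a pre-specified worst rank is acceptable for TTCI. Keep subjects who progress or die as not achieving to the end of the window. Censor only withdrawals and losses, at last contact.
2. **TTCI window.** Reconcile the protocol and SAP into one fixed window, identical in both and ending at neither discharge nor PCR negativity.
3. **NEWS TTCI.** Unless more frequent ward scores are captured in the CRF, report the proportion meeting the criteria by Day 7 and still on Day 15, not a median time or hazard ratio.
4. **Early discharge.** Fix before unblinding how subjects discharged before persistence can be confirmed are scored. Do not count discharge as failure by default, since that could turn fast recoverers into failures. Report the result under both scorings.
5. **PCR time.** Reconcile the swab days (protocol schedule, SAP time frame, Day 28 call). Then use the interval between last positive and first negative swab, allowing for swab day. In 5.3, apply the same method or delete the endpoint as a duplicate of primary endpoint 5.

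The cost is modest SAP rewriting, reconciled windows and swab days, and a less simple analysis. No extra subjects are needed. The Friedman step in 5.3 is a separate minor point.

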5.3 Analysis of Secondary Efficacy Parameters

For Secondary efficacy variables that is Incidence of ICU admissions, subjects survival rate , incidence of mechanical ventilation , percentages of participants with worsening co morbid conditions and changes in clinical comorbid conditions will be analyzed using Chi square test variance (Kruskal Wallis test) for between Groups. If observed mean difference is significant Friedman's post hoc test will be applied to assess which group is significant. Average Time to COVID-19 nucleic acid testing negativity in oropharyngeal/nasal swab) will be assessed at each time points and data will be analyzed by using analysis of variance. If data is not normal, analysis of variance with kruskal wallies will be estimated.

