CLINICAL STUDY PROTOCOL

PROTOCOL TITLE

**A DOUBLE BLIND, RANDOMIZED, PLACEBO CONTROLLED STUDY
TO EVALUATE EFFICACY AND SAFETY OF “VIRACIDE”
IN THE MANAGEMENT OF CORONA VIRUS DISEASE 2019 (COVID-19)**

**Protocol Number: NS-VC-CT01-20
Clinicaltrial.gov ID: NCT04596085**

STUDY SYNOPSIS

Title	A double blind, randomized, placebo controlled study to evaluate efficacy and safety of “ViraCide” in the management of corona virus disease 2019 (COVID-19).
Study Description	
This is a double blind randomized placebo controlled study will be conducted on 124 subjects, 50 years and older with mild or asymptomatic COVID-19. If symptomatic, symptoms are mild (cough, weakness, sore throat, low grade fever 38.50C, respiratory rate should not be more than 22 / min, resting SpO2 >95%, normal highly sensitive C-reactive protein (HS-CRP) (<10mg/L). There are no signs of dehydration, sepsis or shortness of breath.
 
The study will be conducted at two centers. There will be a screening visit at Day -4 followed by three visits at the center at Days 1, 7 and 15 and a follow-up visit on Day 28. All participants will be randomized to receive either ViraCide (investigational product) or matching placebo. All subjects will receive SOC therapy.
 
Note: If subject is discharged before Day 15 PI’s discretion as per patients health condition, then assessments scheduled for Day 15 will be carried out on the discharge day (as far as possible and those not performed will be noted on appropriate CRF page) and Day 15 visit will be done telephonically.

Investigational Product/Study drug	ViraCide softgels given per orally
Comparison product	Matching placebo of ViraCide softgels given per orally
Study Design	Double blind, randomized, placebo controlled study. Subjects will be randomized to the experimental and control groups in a 1:1 ratio. In each group 62 subjects will be recruited, a total of 124 subjects. Subjects of the experimental arm will receive treatment with Study Drug, ViraCide and SOC. The control group will receive matching placebo and SOC. The study consists of the stages of screening, therapy, observation. There will be no switching of subjects between the arms. Participants will receive Study drug or matching placebo for 14 days during the study.
Sample Size	124, including 10% dropouts

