Study Population	
 • 50 years or older • Positive RT- PCR for Sars-Co-V2. • Either asymptomatic or have mild symptoms. Onset of symptoms within no more than 4days • With chronic stable medical conditions: Diabetes Mellitus, or Hypertension, or chronic heart disease.
Study Duration	Total study duration approximately 35 days Screening: 04 days Treatment duration: 14 days Follow-up: 14 days from end of treatment

Number of Sites	02 (two)
Treatment Duration	14 days
Treatment Arms	
Two treatment arms
 
 • Arm A: ViraCide softgels: 3 soft gels, two times every day after breakfast and dinner for 14 days+ SOC Therapy • Arm B: Placebo softgels: 3 soft gels, two times everyday after breakfast and dinner for 14 days + SOC Therapy
Purpose of the study	To study the effectiveness and safety of the Study Drug, ViraCide
	softgels by oral administration compared with placebo softgels in 50 years or older subjects with asymptomatic or mildly symptomatic coronavirus infection (COVID-19) and stable comorbidities.
Objectives	
Primary Objectives
 
1. To evaluate the efficacy of “ViraCide” in the management of mild COVID-19 disease
 
Secondary Objectives
 
1. To evaluate the safety of “ViraCide” in the management of mild COVID-19 disease

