	
Note:
 
*Hematology: Complete blood count (CBC); erythrocyte sedimentation rate (ESR)
 
*Biochemistry:
 
 • Random Blood Sugar, • Serum Creatinine • SGOT, SGPT • Alkaline Phosphatase • Bilirubin-Total/Direct/Indirect • Total Proteins/Albumin/Globulin/A:Gratio • Low density lipoprotein (LDL) Cholesterol(Direct) • LDH • Total Cholesterol • Triglycerides • High Sensitive C-reactive protein(HS-CRP) • BUN (Blood Urea Nitrogen) /Urea • Serum Calcium • Serum Sodium • Serum Potassium • Uric Acid 
*X-ray PA view is an optional test at screening. It may be done

	
at any other time during the study if deemed necessary by the Investigator
 
*Urine pregnancy test (for females only) at screening
 
Note: If subject is discharged before Day 15 PI's discretion as per patients health condition, then assessments scheduled for Day 15 will be carried out on the discharge day (as far as possible and those not performed will be noted on appropriate CRF page) and Day 15 visit will be done telephonically.

Standard of Care Therapy	
SOC therapy for coronavirus infection (COVID-19, SARS-CoV-2) has not been developed yet. Treatment will be given as per the discretion of the PI or as per the guidelines issued by the GOI. GOI guidelines can be accessed here: https://www.mohfw.gov.in/

Concomitant Medications Allowed by the Protocol	
 1. Medications for Diabetes Mellitus 2. Medications for hypertension 3. Statins 4. Blood thinners like aspirin at PI discretion 5. Any medication deemed necessary by the PI to manage the AE/SAE 6. Any other medication deemed necessary by the PI to manage a comorbid condition that is not likely to affect the treatment Protocol
Prohibited Concomitant Medications	Any other herbal medicine or dietary supplement
Statistical Analysis	
Sample size of total 112(56 cases in each arm) completed cases needed to assess the study objective at 80% power and 5% level of significance.
 
Considering 10 % dropout total 124 (62 cases in each arm) cases will be enrolled in this study.

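### SAP 5.3 calls for a Friedman post hoc test between two independent arms, where it does not apply; the step should be deleted and the garbled test wording clarified

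*SAP*

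**What the plan says.** SAP section 5.3 opens with a list: "Incidence of ICU admissions, subjects survival rate , incidence of mechanical ventilation , percentages of participants with worsening co morbid conditions", followed by changes in comorbid condition, whose scale is not defined. These endpoints "will be analyzed using Chi square test variance (Kruskal Wallis test) for between Groups". The wording is garbled: chi-square is named first, the word variance follows without a noun, and Kruskal-Wallis stands in brackets.

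The next sentence sets a conditional step. "If observed mean difference is significant", a Friedman "post hoc test will be applied to assess which group is significant".

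The design is in the Protocol synopsis. The Treatment Arms row gives "Two treatment arms". The Study Design row says "Subjects will be randomized to the experimental and control groups in a 1:1 ratio" and "There will be no switching of subjects between the arms". Neither document describes matching of subjects across arms.

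Elsewhere the SAP handles similar proportions more simply: section 5.2 (progression to severe disease) and section 5.4 (adverse events) name chi-square alone.

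**The concern.** Friedman's test ranks observations within blocks, so it needs matched sets or repeated measurements on the same unit. Here each subject belongs to one arm and contributes one 28-day outcome for ICU admission, survival and ventilation. There are no blocks. To run the test, an analyst would have to pair subjects from different arms by some arbitrary rule, and would have to drop subjects if the arms differed in size.

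The stated purpose also fails. With two arms, a significant comparison already shows which groups differ and in which direction.

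At stake is a second p-value for the same contrast, produced when a secondary result is about to be reported. It may fall on either side of 0.05 depending on the pairing. The SAP does not say which p-value governs, and section 5.3 names no between-arm effect estimate or interval to settle the matter.

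**Working it through.** **Inputs from the documents.** Two independent arms, 1:1. The Protocol's Statistical Analysis row gives 112 "completed cases needed to assess the study objective at 80% power and 5% level of significance", that is 56 per arm, and 124 enrolled (62 per arm) after 10% dropout. The enrolment figure reproduces by multiplying up: 112 × 1.10 = 123.2, rounded up to 124. The 112 cannot be re-derived because no effect size or rate is given. The point does not depend on either figure.

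**Assumption.** The documents give no event rates, so the counts below are illustrative. Some lie close to p = 0.05 and some do not.

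**Step 1: Kruskal-Wallis on yes/no data.** With two arms, H = Pearson chi-square × (N − 1)/N. At N = 112 the factor is 111/112 = 0.991. For 3 v 10 events, chi-square = 4.264 (p = 0.0389) and H = 4.264 × 0.991 = 4.226 (p = 0.0398). The second test is redundant and changes nothing material.

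**Step 2: Friedman on arbitrarily paired yes/no data.** With a and b events in the two arms and k pairs in which both members have the event, the tie-corrected statistic is

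F = (b − a)² / (a + b − 2k), on 1 degree of freedom.

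The event totals fix the numerator, but k depends on who is paired with whom. Under random pairing, k is hypergeometric.

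For 3 v 10:
- k = 0: F = 49/13 = 3.77, p = 0.052. Probability 55%.
- k = 3 (the maximum): F = 49/7 = 7.00, p = 0.008.

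For 20 v 31:
- k = 0: F = 121/51 = 2.37, p = 0.1235.
- k = 20 (the maximum): F = 121/11 = 11.0, p = 0.0009.

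These are the exact extremes; the end values are very unlikely under random pairing.

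**Results at 56 per arm (assumed counts).**

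| Events | Chi-square p | Friedman p, range over pairings | Pairings with p > 0.05 |
|---|---|---|---|
| 3 v 10 | 0.039 | 0.008 to 0.052 | 55% |
| 7 v 16 | 0.035 | 0.003 to 0.061 | 8% |
| 20 v 31 | 0.037 | 0.0009 to 0.12 | 19% |
| 5 v 14 | 0.024 | 0.003 to 0.039 | none |
| 0 v 5 | 0.022 | 0.025 (fixed) | none |

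With no events in one arm, k can only be 0, so F = 25/5 = 5.0 whatever the pairing. At 62 per arm the share above 0.05 is 58% for 3 v 10 and 39% for 20 v 31.

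**Step 3: a continuous comorbidity measure.** In one simulated data set of 56 per arm (normal, SD 1, true shift 0.5), Kruskal-Wallis gave p = 0.0003. Over 3,000 random pairings Friedman p ran from below 0.0001 to 0.285, and was below 0.05 in 97% of them. This is one example, not an estimate of how often results would change.

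**Step 4: is chi-square adequate as the single test?** An exact check at 56 per arm puts the maximum type I error of the Pearson test at 5.2%, so it can stay.

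**The case against.** The strongest reply concerns what the garbled text means. Words seem to be missing after chi-square. A natural reading is chi-square for the four yes/no endpoints, with analysis of variance or Kruskal-Wallis for change in comorbid condition. The Friedman trigger, a significant mean difference, also fits a measured variable better than a proportion. This stands as far as it goes: the text does not establish that Kruskal-Wallis, or the Friedman step, was meant for every yes/no endpoint. It does not rescue the step, because Friedman has no blocks between these arms for a continuous measure either. The sentence gives its purpose as finding which group is significant, so it cannot be read as a within-subject analysis over visits.

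Three further limits stand:
- Pairing matters only when both arms have events. In asymptomatic or mild disease, death and ventilation may be too rare for that.
- A change of side at 0.05 needs a first result near 0.05; 5 v 14 never crosses.
- The documents describe no data layout, so pairing by file order is only one way the step might be carried out.

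A reader might infer that Friedman could overturn a valid chi-square result. The SAP does not say so: nothing lets the follow-up replace the first test, it cannot create a finding where the first test is negative, and the table list contains no Friedman table. The gap is that the SAP is silent on which p-value governs.

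**Conclusion.** The point holds in limited form. The Friedman step is inapplicable to two independent arms and answers no question that two arms leave open. If it were run, its p-value would depend on an arbitrary pairing whenever both arms have events. In the assumed cases the share of pairings above 0.05 ranges from none to 55% at 56 per arm. Those shares rest on invented counts and random pairing; they show the mechanism and do not predict this trial's results.

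The Kruskal-Wallis wording is a clarity fault only. The primary endpoints are untouched, and the step follows only a significant first test. It should still be corrected before analysis: a prespecified step must otherwise be followed, giving an arbitrary p-value, or dropped after the results are known.

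**What to change.** In SAP section 5.3:

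1. Delete the sentence that calls for Friedman's post hoc test.
2. For the four yes/no endpoints, name the chi-square test as the only between-arm test, and report the risk difference with its 95% CI.
3. State whether change in comorbid condition is categorical or continuous. For any continuous measure, name one two-sample test, such as the rank test, and remove Kruskal-Wallis from the yes/no endpoints.

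The cost is SAP wording only. Sample size, data collection and visits do not change.
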